#### **8.4.5.2. Exposure During Breastfeeding**

An EDB occurs if:

- A female participant is found to be breastfeeding within 28 days after receiving the study intervention.

- A female nonparticipant is found to be breastfeeding while being exposed or having been exposed to study intervention (ie, environmental exposure). An example of environmental EDB is a female family member or healthcare provider who reports that she is breastfeeding after having been exposed to the study intervention by needlestick injury, inhalation, or skin contact.

The investigator must report EDB to Pfizer Safety within 24 hours of the investigator's awareness, irrespective of whether an SAE has occurred. The information must be reported using via PSSA. When EDB occurs in the setting of environmental exposure, the exposure information does not pertain to the participant enrolled in the study, so the information is not recorded on a CRF. However, a copy of the completed report is maintained in the investigator site file.

An EDB report is not created when a Pfizer drug specifically approved for use in breastfeeding women (eg, vitamins) is administered in accordance with authorized use. However, if the infant experiences an SAE associated with such a drug, the SAE is reported together with the EDB.

#### **8.4.5.3. Occupational Exposure**

The investigator must report any instance of occupational exposure to Pfizer Safety within 24 hours of the investigator's awareness via PSSA, regardless of whether there is an associated SAE. Since the information about the occupational exposure does not pertain to a participant enrolled in the study, the information is not recorded on a CRF; however, a copy of the completed Vaccine SAE Report Form must be maintained in the investigator site file.

#### **8.4.6. Cardiovascular and Death Events**

Not applicable.

#### **8.4.7. Disease-Related Events and/or Disease-Related Outcomes Not Qualifying as AEs or SAEs**

A potential COVID-19/MIS-C illness visit, potential COVID-19 illnesses, and their sequelae should not be recorded as AEs, with the exception of those assessed by the investigator as related to the study intervention or those meeting the criteria for SAEs. These data will be captured as efficacy assessment data only on the relevant pages of the CRF, as these are expected endpoints.

All SAEs occurring in a participant during the active collection period as described in [Section 8.4.1](#) will be reported to Pfizer Safety via PSSA immediately upon awareness, and under no circumstance should this exceed 24 hours, as indicated in [Appendix 3](#). This includes potential COVID-19 illnesses and their sequelae that meet the definition of an SAE.

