#### **10.9.8.5.8. COVID-19 and MIS-C Surveillance**

If a participant experiences any of the following (irrespective of perceived etiology or clinical significance), the participant or his/her parent(s)/legal guardian is instructed to contact the site immediately. If confirmed to be a potential COVID-19 illness, the site should schedule and conduct either an in-person or telehealth visit as soon as possible, optimally within 3 days after symptom onset (and at the latest 4 days after symptom resolution). Refer to [Section 10.9.8.2.1](#) for more details on COVID-19 and MIS-C surveillance.

- A diagnosis of COVID-19;
- Fever;
- New or increased cough;

- New or increased shortness of breath;
- Chills;
- New or increased muscle pain;
- New loss of taste/smell;
- Sore throat;
- Diarrhea;
- Vomiting.

Note that:

- The CDC list of COVID-19 symptoms can be found at: <https://www.cdc.gov/coronavirus/2019-ncov/symptoms-testing/symptoms.html>. The additional symptoms listed by the CDC (ie, those not listed in the above protocol-defined list) should not trigger a potential COVID-19 illness visit unless, in the opinion of the PI, deemed necessary.
- If new symptoms are reported within 4 days after resolution of all previous symptoms, they will be considered to be part of a single illness and a second illness visit is not required.
- Surveillance of potential COVID-19 symptoms should continue even if a participant has a positive SARS-CoV-2 test earlier in the study.

During the 7 days following the vaccination, potential COVID-19/MIS-C symptoms that overlap with specific systemic events (ie, fever, chills, new or increased muscle pain, diarrhea, vomiting) should not trigger a potential COVID-19 illness visit unless, in the investigator's opinion, the clinical picture is more indicative of a possible COVID-19 illness than vaccine reactogenicity. If, in the investigator's opinion, the symptoms are considered more likely to be vaccine reactogenicity, but a participant is required to demonstrate that he or she is SARS-CoV-2–negative, a local SARS-CoV-2 test may be performed. If the test result is positive, the symptoms should be recorded as a potential COVID-19 illness; if not, the symptoms that overlap with systemic events should be recorded in the reactogenicity e-diary or as AEs, if not captured in the reactogenicity e-diary.

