#### **10.9.8.5.9. Potential COVID-19 Illness Visit (Optimally Within 3 Days After Potential COVID-19 Illness Onset)**

This visit may be conducted as an in-person or telehealth visit; a telehealth visit involves the sharing of healthcare information and services via telecommunication technologies (eg, audio, video, videoconferencing software) remotely, thus allowing the participant and investigator to communicate on aspects of clinical care.

As a participant's COVID-19 illness may evolve over time, several contacts may be required to obtain the following information:

- Record details of any of the prohibited medications specified in [Section 10.9.6.9.1](#) received by the participant if required for his or her clinical care.
- Record nonstudy vaccinations as described in [Section 10.9.6.9](#).
- Record AEs as described in [Section 8.4](#). Note: Potential COVID-19/MIS-C illnesses with their sequelae should not be recorded as AEs, with the exception of those assessed by the investigator as related to study intervention or those meeting the criteria for SAEs.
- If the visit is conducted in person, obtain a nasal (midturbinate) swab (collected by site staff). Alternatively, if conducted by telehealth, instruct the participant or his/her parent(s)/legal guardian to self-collect a nasal (midturbinate) swab at home and ship it for assessment at the central laboratory.
- Collect COVID-19–related standard-of-care clinical and laboratory information. This includes, but is not limited to:
  - Symptoms and signs, including
    - Clinical signs at rest indicative of severe systemic illness (RR  $\geq$ 30 breaths per minute, HR  $\geq$ 125 beats per minute, SpO2  $\leq$ 93% on room air at sea level, or PaO2/FiO2  $<$ 300 mm Hg).
    - Evidence of shock (SBP  $<$ 90 mm Hg, DBP  $<$ 60 mm Hg, or requiring vasopressors).
    - Significant acute renal, hepatic, or neurologic dysfunction.

- Respiratory failure (defined as needing high-flow oxygen, noninvasive ventilation, mechanical ventilation, or ECMO).
- Clinical diagnosis.
- Local laboratory SARS-CoV-2 test result(s). Note that if it is routine practice to perform a repeat local SARS-CoV-2 test for any reason, then a repeat nasal (midturbinate) swab should also be obtained and shipped for assessment at the central laboratory.
- Full blood count.
- Blood chemistry, specifically creatinine, urea, LFTs, and CRP.

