#### **10.9.8.5.10. SARS-CoV-2 NAAT Results**

Nasal (midturbinate) swabs for SARS-CoV-2 NAAT are obtained at:

- Visit C1: Contributes to the determination of a participant's baseline SARS-CoV-2 infection status.
- Potential COVID-19 illness visits: To determine whether symptoms experienced by the participant fulfill the COVID-19 case definition.

Research laboratory-generated positive results from the vaccination visit swabs, and all results from the illness visit swabs, will be provided to the site at the end of the study and, therefore, cannot be relied upon to direct clinical care. The participant or his/her parent(s)/legal guardian should be directed to seek additional testing through the participant's primary healthcare provider at a licensed clinical laboratory when the participant is exhibiting potential COVID-19 symptoms or otherwise receiving a positive result and counseled on whether to take any precautionary measures pending confirmatory testing, as per local guidance.

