6.1.1.3. Adverse Events

6.1.1.3.1. Main Analysis

- Estimand: The percentage of participants reporting AEs from the study vaccination through 1 month after the study vaccination ([Section 2.2](#)).
- Analysis set: Safety population ([Section 4](#)).
- Analysis time point: From the study vaccination through 1 month after the study vaccination.
- Analysis methodology: Descriptive statistics ([Section 5.2.1](#) and [Section 3.1.1.3](#)).
- Intercurrent events and missing data: Missing data will not be imputed, except for partial AE start dates ([Section 5.3](#)).
- Reporting results: Counts, percentages, and the associated 2-sided Clopper-Pearson 95% CIs of AEs within 1 month after the study vaccination will be provided for each age subgroup (12-17 years [for Cohort 2 only], 18-55 years, >55 years) and overall.

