6.4.2. COVID-19 Cases**6.4.2.1. Cohort 1 and Cohort 2 combined, Cohort 3**

Confirmed COVID-19 cases, confirmed severe COVID-19 cases, and strain sequencing of the COVID-19 cases will be summarized.

6.4.3. SARS-CoV-2–Neutralizing Titers for Emerging Variants**6.4.3.1. Cohort 1 and Cohort 2 combined, Cohort 3**

- Estimands:
 - GMTs of SARS-CoV-2–neutralizing titers for emerging variants (under monitoring, of interest, and/or of concern) not already specified at specific time points for each age subgroup (12-17 years [for Cohort 2 only], 18-55 years, >55 years).
 - GMFRs of SARS-CoV-2–neutralizing titers for emerging variants (under monitoring, of interest, and/or of concern) not already specified from before the study vaccination to each subsequent time point for each age subgroup (12-17 years [for Cohort 2 only], 18-55 years, >55 years).
 - Percentages of participants with seroresponse to SARS-CoV-2–neutralizing titers for emerging variants (under monitoring, of interest, and/or of concern) not already specified at each time point for each age subgroup (12-17 years [for Cohort 2 only], 18-55 years, >55 years).

- Analysis set, analysis methodology, and intercurrent events and missing data are the same as described above for the immunogenicity primary endpoint ([Section 6.1.2.1](#)).
- Reporting results: GMTs at each time point and GMFRs of SARS-CoV-2–neutralizing titers for emerging variants from before the study vaccination to each subsequent time point after the study vaccination, along with the associated 2-sided 95% CIs, will be provided for each age subgroup and overall. The percentages of participants with seroresponse at each time point after the study vaccination, and the associated Clopper-Pearson 95% CIs, will be provided for each age subgroup (12-17 years [for Cohort 2 only], 18-55 years, >55 years) and overall.

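### Nonserious, unrelated potential COVID-19 illnesses that prove NAAT-negative enter no planned AE or COVID-19 summary, so the primary AE percentage can only be understated

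*Protocol*

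**What the plan says.** Protocol 8.4.7 states that "potential COVID-19 illnesses, and their sequelae should not be recorded as AEs". The same sentence makes two exceptions, one for relatedness and one for seriousness; the bar applies "with the exception of those assessed by the investigator as related to the study intervention or those meeting the criteria for SAEs". The section then says where the remaining illnesses go and why: "These data will be captured as efficacy assessment data only on the relevant pages of the CRF, as these are expected endpoints".

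The illness-visit sections repeat the bar with the same two exceptions (10.7.8.5.8 for Substudy A, 10.8.8.5.8 for B, 10.9.8.5.9 for C): "Potential COVID-19/MIS-C illnesses with their sequelae should not be recorded as AEs". None of these texts mentions the swab result.

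The surveillance sections (10.7.8.5.7, 10.8.8.5.7, 10.9.8.5.8) set a wide entry point. They begin "If a participant experiences any of the following (irrespective of perceived etiology or clinical significance"), and then list a COVID-19 diagnosis and single symptoms such as fever, cough, sore throat, diarrhea, vomiting and muscle pain. The participant contacts the site, and a visit follows if the site confirms a potential COVID-19 illness.

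The primary AE estimand in both SAPs (6.1.1.3.1) is: "The percentage of participants reporting AEs from the study vaccination through 1 month after the study vaccination". The COVID-19 analysis (SAP for Substudies A and B, 6.2.2; SAP for Substudy C, 6.4.2) is: "Confirmed COVID-19 cases, confirmed severe COVID-19 cases, and strain sequencing of the COVID-19 cases will be summarized".

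**The concern.** The exemption rests on these illnesses being endpoints, but it is written for potential illnesses and the endpoint is confirmed illness. A participant with cough and fever on Day 15, judged unrelated and not serious, with a negative swab, is kept off the AE page by 8.4.7 and is not a COVID-19 case in either SAP. No planned table shows the event.

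At stake is a primary safety endpoint. The AE percentage through 1 month would leave out a class of intercurrent illness that the estimand does not say is left out. Whether a nonserious illness of this kind counts would turn on the investigator's view of relatedness, in an open-label study.

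**Working it through.** The plan gives no figure for this point, so the check is mainly of text.

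**1. Does the bar depend on the swab?** No. The exceptions in 8.4.7 and the illness-visit sections are relatedness and seriousness only.

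**2. Can a NAAT-negative illness be a case?** Not a confirmed COVID-19 case. The definition (10.7.8.2.1, 10.8.8.2.1, 10.9.8.2.1) requires at least one symptom and a positive NAAT around the symptomatic period. MIS-C can be met on exposure without a positive test, but its definition requires hospitalization, so it would be recorded as serious.

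**3. Is there a route back to the AE page?** One. In the 7 days after vaccination, if symptoms are thought more likely to be reactogenicity and a local test is done and is not positive, the symptoms that overlap with systemic events (fever, chills, muscle pain, diarrhea, vomiting) go to the e-diary or, if not captured there, to AEs (10.7.8.5.7, 10.8.8.5.7, 10.9.8.5.8). The gap that remains is:
- any listed symptom after that week and within the 1-month AE window;
- cough, sore throat, shortness of breath and loss of taste or smell at any time in the window.

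**4. Could sites reclassify on the central result?** Not in time. Under the NAAT results sections (10.7.8.5.9, 10.8.8.5.9, 10.9.8.5.10), "all results from the illness visit swabs, will be provided to the site at the end of the study". No section provides for reclassification.

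**5. Do other sections agree with 8.4.7?** No. Section 8.4.1.2 calls for all nonserious AEs in the collection period to be recorded. Section 10.3.1 exempts the disease being studied, which a NAAT-negative illness has not been shown to be.

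**6. Direction.** The rule removes participants from the numerator, adds none, and leaves the denominator (the safety population) unchanged. The AE percentage can only fall.

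**7. Size.** The documents give no rate r of nonserious, unrelated, NAAT-negative illness handled as potential COVID-19 in the 1-month window. Taking r as an assumption and N as planned enrollment, expected participants affected = N × r:

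| Group | N | r = 1% | 3% | 5% | 10% |
|---|---|---|---|---|---|
| Substudy A | 400 | 4 | 12 | 20 | 40 |
| Substudy B | 300 | 3 | 9 | 15 | 30 |
| Substudy C, Cohorts 1 and 2 | 200 | 2 | 6 | 10 | 20 |
| Substudy C, Cohort 3 | 100 | 1 | 3 | 5 | 10 |

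For example, 400 × 0.01 = 4 and 400 × 0.10 = 40. On these assumptions the any-AE percentage is understated by at most 100 × r percentage points. These are upper bounds, because a participant with another recorded AE is already counted.

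**The case against.** The other side has several good points.

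- **Exceptions.** A reader who stops at the bar might infer that every potential COVID-19 illness is excluded. The same sentence keeps related and serious illnesses in AE recording whatever the swab shows. This stands, and limits the point to nonserious illnesses judged unrelated.
- **Entry.** A symptom prompts contact; the visit follows only after the site confirms a potential COVID-19 illness, and 10.7.8.2.1, 10.8.8.2.1 and 10.9.8.2.1 speak of acute respiratory illness. Isolated gastrointestinal symptoms may not always enter. This stands, but no criterion for the site's step is given, so it narrows the gap by an unknown amount.
- **Other information at the site.** The illness visit collects the clinical diagnosis and local test results, and 10.3.3 wants the diagnosis recorded as the AE where possible. A site with another diagnosis might make an AE entry. These general provisions, and 8.4.1.2, do not override the explicit bar in 8.4.7; at best the texts conflict and practice may differ between sites.
- **Data loss.** A reader might infer that the illnesses vanish from the database. They do not: symptoms and diagnosis are on the illness-visit pages. They are absent from planned summaries.
- **Consequence.** The AE endpoint is descriptive, with Clopper-Pearson intervals. No test, margin or power figure depends on it. This stands.
- **Remedy.** Limiting the exemption at the site to confirmed cases cannot be relied on in real time, because central results come too late. Counting these events in the primary percentage itself could be a major modification needing a protocol amendment under Protocol Section 9. Both stand, and they shape the fix.

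**Conclusion.** The point holds in a limited form. Nonserious potential COVID-19 illnesses that are judged unrelated and prove NAAT-negative have no route into a planned AE or COVID-19 summary, apart from the narrow first-week provision. The reason given in 8.4.7 does not fit them. The primary AE percentage through 1 month can only be understated, in all three substudies.

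The amount cannot be estimated from the documents. Across an assumed 1% to 10%, the most that could be missing is 4 to 40 participants in Substudy A, 3 to 30 in B, 2 to 20 in Cohorts 1 and 2 of C, and 1 to 10 in Cohort 3. These bounds assume that sites follow 8.4.7 as written and that planned enrollment is reached.

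A reader might go further and infer that the reported AE percentage is some definite fraction of the true one, such as half. That needs both an illness rate and a background AE rate, and the documents give neither. SAE reporting, the Substudy B noninferiority tests and the confirmed COVID-19 counts are untouched. This is a worthwhile, inexpensive improvement to a descriptive endpoint.

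**What to change.** **In both SAPs.** Add a supplementary analysis to the primary AE section:
- Once NAAT results are available, the sponsor identifies illness-visit records with onset from vaccination through 1 month that do not meet the confirmed COVID-19 or MIS-C definition.
- Code them in MedDRA from the recorded diagnosis or, failing that, the symptoms.
- Report the AE percentage with and without them, by age subgroup and overall, with Clopper-Pearson intervals.
- Give no AE intensity for these records where it was not collected.
- Label the analysis post hoc for Substudies A and B, since Protocol 2.2.1 already describes results from both.

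The primary percentage stays as defined, with the supplementary one beside it.

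**In the protocol.** Reconcile 8.4.7, 8.4.1.2, 10.3.1 and the surveillance sections (10.7.8.5.7, 10.8.8.5.7, 10.9.8.5.8), so that the exemption matches its stated reason, and say how an illness later found not to be COVID-19 is handled. Because sites lack timely central results, that step belongs with the sponsor.

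**Cost.** SAP and protocol wording, and coding of data already collected; no new visit or procedure. The downside is the extra coding and a somewhat higher supplementary AE percentage.

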#### **8.4.8. Adverse Events of Special Interest**

Refer to the appendix of each substudy.

#### 8.4.9. Medical Device Deficiencies

Not applicable.

#### 8.4.10. Vaccination Errors

Vaccination errors may result from the administration or consumption of the study intervention by the wrong participant, or at the wrong time, or at the wrong dosage strength.

Vaccination errors are recorded and reported as follows:

Recorded on the Vaccination Error Page of the CRF	Recorded on the Adverse Event Page of the CRF	Reported via PSSA to Pfizer Safety Within 24 Hours of Awareness
All (regardless of whether associated with an AE)	Any AE or SAE associated with the vaccination error	Only if associated with an SAE

Vaccination errors include:

- Vaccination errors involving participant exposure to the study intervention;
- Potential vaccination errors or uses outside of what is foreseen in the protocol that do or do not involve the study participant;
- The administration of expired study intervention;
- The administration of an incorrect study intervention;
- The administration of an incorrect dosage;
- The administration of study intervention that has undergone temperature excursion from the specified storage range, unless it is determined by the sponsor that the study intervention under question is acceptable for use.

Such vaccination errors occurring to a study participant are to be captured on the vaccination error page of the CRF, which is a specific version of the AE page.

Whether or not the vaccination error is accompanied by an AE, as determined by the investigator, the vaccination error is recorded on the vaccination error page of the CRF and, if applicable, any associated AE(s), serious and nonserious, are recorded on the AE page of the CRF.

In the event of a vaccination dosing error, the sponsor should be notified within 24 hours.

Vaccination errors should be reported to Pfizer Safety within 24 hours via PSSA **only when associated with an SAE**.

## 8.5. Pharmacokinetics

Pharmacokinetic parameters are not evaluated in this study.

## 8.6. Genetics

### 8.6.1. Specified Genetics

One or more substudies may include collection of blood samples for PBMC isolation and HLA typing; these blood samples may be used for DNA and/or RNA isolation. The DNA and/or RNA samples from the PBMC isolation may be used for sequencing of participants' antibody and/or BCR heavy-chain and light-chain genes, TCR genes, and/or mRNAs, for understanding the B-cell, T-cell, and antibody repertoires. The DNA and/or RNA samples from the blood sample for HLA typing may be used to further characterize HLA type.

See Appendix 5 ([Section 10.5](#)) for information regarding genetic research. Details on processes for collection and shipment of these samples will be provided separately.

## 8.7. Biomarkers

Biomarkers are not evaluated in this study.

## 8.8. Immunogenicity Assessments

Immunogenicity assessments are described in the appendices of each substudy.

## 8.9. Health Economics

Health economics/medical resource utilization and health economics parameters are not evaluated in this study.

## 8.10. Study Procedures

See [Section 10.7.8.5](#) for Substudy A procedures.

See [Section 10.8.8.5](#) for Substudy B procedures.

See [Section 10.9.8.5](#) for Substudy C procedures.

## 9. STATISTICAL CONSIDERATIONS

Methodology for summary and statistical analyses of the data collected in this study is described here and further detailed in the SAP, which will be maintained by Pfizer. The SAP may modify what is outlined in the protocol where appropriate; however, any major modifications of the primary endpoint definitions or their analyses will also be reflected in a protocol amendment.

